9.2.2. Secondary endpoints

Efficacy endpoint

- Time to treatment failure (TTF) of avelumab

Definition of TTF is provided in 20. The following avelumab treatment data will be collected:

- 1) Date of start and end of avelumab administration
- 2) Dosage of avelumab
- 3) Date of avelumab discontinuation and interruption
- 4) Reason for avelumab discontinuation and interruption
- 5) Date of last survival confirmation

- Real-world progression-free survival (rwPFS)

Definition of rwPFS is provided in 20. The following data will be collected:

- 1) Date of start of avelumab treatment (administration)
- 2) Date of first disease progression or death due to any cause, whichever came first
- 3) Date of last survival confirmation

- Objective Response Rate (ORR)

ORR is defined in 21. The following data will be collected:

- 1) Tumor assessment (CR, PR, SD, PD)

- rwPFS from chemotherapy (rwPFS-c)

Definition of rwPFS-c is provided in Section 9.2.3.4. The following data will be collected:

- 1) Date of start of 1L Cht (administration)

- 2) Date of first disease progression or death due to any cause during avelumab treatment, whichever came first
- 3) Date of last survival confirmation

Safety endpoints

- Corticosteroid therapy for immune-related adverse events (irAEs)
The following data will be collected:
 - 1) Date of treatment
 - 2) Drug name of corticosteroid
 - 3) Starting dose of corticosteroid
 - 4) Duration of corticosteroid treatment
- Premedication for potential infusion-related reaction of avelumab
The following data will be collected:
 - 1) Presence of premedication for infusion-related reaction of avelumab
 - 2) Drug name used for premedication for infusion-related reactions of avelumab
- Treatment for infusion-related reaction of avelumab
The following data will be collected:
 - 1) Presence of treatment for infusion-related reaction of avelumab
 - 2) Drug name used for treatment for infusion-related reaction of avelumab
- Regimen after avelumab maintenance therapy
The following data will be collected:
 - 1) Medication for UC after avelumab maintenance therapy (drug name, start date of treatment, end date of treatment)
- Hematological test (after the start of 1L Cht)
The following data will be collected:
 - 1) Red blood cell count/ hemoglobin/ hematocrit/ white blood cell count (neutrophils, eosinophils, basophils, monocytes, lymphocytes)/ platelet count/ C-reactive protein (CRP)/ total protein/ albumin/ AST/ ALT/ LDH/ BUN/ creatinine/ Na/ K/ Cl

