9.2.3. Definition of endpoints

9.2.3.1. Time to treatment failure (TTF)

TTF is defined as the following:

TTF, defined as the time from start of avelumab maintenance therapy to the date of end of treatment due to any cause including death. If there is no record of the end of treatment, it be discontinued on the last observation date during the study period.

9.2.3.2. rwPFS

rwPFS is defined as the following:

The time from start of avelumab maintenance therapy to date of first disease progression (as

clinically assessed by local investigator based on radiology, laboratory evidence, pathology, or other assessments) or death due to any cause, whichever occurred first. If there were no clinical records of death or disease progression, they will be censored at the date of initiation of the next line of therapy for the patients undertaking 2 or more lines of therapy (subsequent therapy after avelumab maintenance therapy) based on the record, or at their last observation date during the study period for the patients undertaking only 1 line of therapy (only avelumab maintenance therapy) based on the record.

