9.2.3.3. Objective response rate (ORR)

OR is defined as the following:

Complete or partial response as the best adjudication result (CR > PR > SD > PD) in a method that complies with Response Evaluation Criteria in Solid Tumors (RECIST) version. 1.1 tumor assessment as closely as possible in clinical practice by investigator's judgment.

9.2.3.4. rwPFS-c

rwPFS-c is defined as the following:

The time from start of 1L Cht to date of first disease progression (as clinically assessed by local investigator based on radiology, laboratory evidence, pathology, or other assessments) or death due to any cause during avelumab treatment, whichever occurred first. If there were no clinical records of death or disease progression, they will be censored at the date of initiation of the next line of therapy for the patients undertaking 2 or more lines of therapy (subsequent therapy after avelumab maintenance therapy) based on the record, or at their last observation date during the study period for the patients undertaking only 1 line of therapy (only avelumab maintenance therapy) based on the record.

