5.5 Derived variable

The items and definitions of variables whose derivation is necessary at the time of statistical analysis are shown below.

Continuous variable

Item	Derivation method
Treatment-free interval: Time from the end date of first-line chemotherapy to the start date of avelumab administration (days)	Start date of initial administration with avelumab – end date of first-line chemotherapy administration + 1
Duration of treatment of first-line chemotherapy (days)	End date of first-line chemotherapy administration – start date of first-line chemotherapy administration + 1
Duration of treatment (irAE treatment) of corticosteroid (days)	End date of corticosteroid administration – start date of corticosteroid administration + 1
Time to treatment failure of avelumab (TTF)	Defined as the period from the date of start of avelumab to the date of end of treatment* for any reasons including death. If there is no record of end of treatment, patients will be censored at the date of last observation during the study period. *The following sensitivity analysis will also be performed. Considering its clinical meaning, "interruption due to being well-controlled" does not correspond to "treatment failure"; it should be treated as an event on the day when the death or discontinuation was observed prior to the last observation date. If no death or discontinuation occurred before the date of the last observation, data will be censored at the date of the last observation.
Real-world progression-free survival (rwPFS)	Defined as the period from the start date of avelumab maintenance therapy to the date of first

	
disease progression (clinical evaluation based on imaging examinations, laboratory tests, and pathological tests, as well as other evaluations by the investigators of each institution) or death from any cause, whichever occurs earlier.
 
If there is no record of death or disease progression, patients on second or later lines (following avelumab maintenance therapy) will be censored at the start of the second-line treatment, and patients on only avelumab maintenance therapy will be censored at the date of the last visit during the study, based on the medical record.

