Real-world progression-free survival from chemotherapy (rwPFS-c)	
Defined as the period from the start date of first-line chemotherapy to the date of first disease progression (clinical evaluation based on imaging examinations, laboratory tests, and pathological test, as well as other evaluations by the investigators of each institution) or death from any cause, whichever occurs earlier.
 
If there is no record of death or disease progression, patients on second or later lines (following avelumab maintenance therapy) will be censored at the start of the second-line treatment, and patients on only avelumab maintenance therapy will be censored at the date of the last visit during the study, based on the medical record.

Starting dose of corticosteroid (Steroid equivalent dose)	Calculate according to “5.4 Steroid equivalent dose (prednisolone-equivalent dose.”
Duration of treatment of corticosteroid (days)	Last administration date – date of first administration of the first steroid drug + 1
Duration of treatment of avelumab maintenance (days)	Last administration date – date of first administration + 1.
Duration of treatment of each regimen (days)	Last administration date – date of first administration + 1.

Categorical variable

Item	Derivation method
Age (2 divisions)	Age is divided into the following categories: <65 years/65 years or older
Site of primary tumor (2 divisions)	The primary site is divided into the following categories: "upper urinary tract" for renal pelvis or ureter "lower urinary tract" for bladder and urethra
Tumor histological type (2)	The histological types are divided into the following categories. "Urothelial carcinoma" for urothelial carcinoma "Non-urothelial carcinoma" for adenocarcinoma, squamous cell carcinoma, small cell carcinoma, or others
Presence or absence of visceral metastasis	"Presence" will be selected if the metastatic site is "lung," "liver," "adrenal gland," "pancreas," "kidney," "spleen," or "other" which is regarded as visceral metastasis. If the metastatic site is not regarded as visceral metastasis, "absence" will be selected.
Presence or absence of non-visceral metastasis	"Presence" will be selected if the metastatic site is "bone," "distant lymph nodes," or "other" which is regarded as non-visceral metastasis. If the metastatic site is not regarded as non-visceral metastasis, "absence" will be selected.

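### Protocol and SAP define the rwPFS-c death event and the rwPFS and rwPFS-c censoring date differently, and SAP 8.1.4 measures the study's observation period from chemotherapy start

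*SAP*

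**What the plan says.** **Death event for rwPFS-c.** Protocol 9.2.3.4 ends the interval at progression "or death due to any cause during avelumab treatment, whichever occurred first". The collection list in Protocol 9.2.2 carries the same limit: "Date of first disease progression or death due to any cause during avelumab treatment, whichever came first". SAP 5.5 sets the clock with "Defined as the period from the start date of first-line chemotherapy to the date of first disease progression" and counts death from any cause, with no on-treatment limit. For rwPFS, Protocol 9.2.3.2 has no such limit either ("or death due to any cause, whichever occurred first"), and SAP 5.5 agrees.

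**Censoring date for rwPFS and rwPFS-c.** Both documents censor at the start of the next line where there is one. Where there is none, Protocol 9.2.3.2 and 9.2.3.4 say "or at their last observation date during the study period for the patients undertaking only 1 line of therapy". SAP 5.5 says for both endpoints that such patients "will be censored at the date of the last visit during the study". For TTF the same SAP section says "patients will be censored at the date of last observation during the study period".

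**Observation period.** Protocol 6 and 9.1 and SAP 3.3 run it from the index date (first avelumab prescription) to 30 June 2022. SAP 8.1.4 sets out to evaluate the study's overall observation period by reverse Kaplan-Meier within the rwPFS-c analysis, whose time zero is chemotherapy start. SAP 8.1.1 and 8.1.2 repeat the sentence for TTF and rwPFS.

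**The concern.** A reader of the report must be able to tell which deaths ended rwPFS-c and when event-free patients left the risk set. At present the answer depends on the document consulted. A death after avelumab has stopped, without recorded progression, is an event under the SAP but not under the protocol's rwPFS-c wording. Within the protocol, the same death is an event for rwPFS.

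The two censoring dates may differ for patients whose later status comes from another facility or from a survival check without a visit.

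The follow-up figure matters because readers use it to judge the maturity of the Kaplan-Meier curves. A figure that includes the months before avelumab overstates the follow-up on treatment and afterwards. The plan as written also yields three estimates of one named quantity.

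**Working it through.** **1. The plan's own follow-up figure.** Inputs: index dates 24 February to 30 November 2021 and cut-off 30 June 2022 (Protocol 6, 9.1). SAP 5.3 counts days as target minus start plus 1, with 30 days per month.
- Shortest: 30 Nov 2021 to 30 Jun 2022 = 212 + 1 = 213 days; 213/30 = 7.1 months. This reproduces the protocol's minimum of 7 months.
- Longest: 24 Feb 2021 to 30 Jun 2022 = 491 + 1 = 492 days; 492/30 = 16.4 months. No observation period from the index date can exceed this.

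**2. Observation period on the two axes.** The documents give no lead-in or event rate, so the rest of this step is illustration. Assumptions: follow-up uniform on 213 to 492 days; rwPFS exponential with median 4, 6 or 9 months; lead-in = chemotherapy duration plus treatment-free gap, each uniform, in weeks.
- Index-date axis: the reverse Kaplan-Meier median should equal the median of the follow-up distribution, (213 + 492)/2 = 352.5 days = 11.75 months. Simulation gives 11.7 to 11.8.
- Chemotherapy axis: roughly 11.75 plus the median lead-in.

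| Lead-in (weeks) | Median lead-in (months) | 11.75 + lead-in | Simulated |
|---|---|---|---|
| U(12,18) + U(0,4) | 17 × 7/30 = 4.0 | 15.7 | 15.7–15.8 |
| U(12,18) + U(4,10) | 22 × 7/30 = 5.1 | 16.9 | 16.9–17.0 |
| U(18,24) + U(4,10) | 28 × 7/30 = 6.5 | 18.3 | 18.3–18.4 |

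The excess over the index-date median is about 4.0 to 6.6 months.

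**3. Does the chemotherapy-axis figure pass the 16.4-month maximum?** Step 2 follows every event-free patient to cut-off, but the plan also censors at next-line start and, in the SAP, at the last visit. Suppose 10% of events are replaced by next-line censoring just beforehand and the last visit falls on average 0.5 month before cut-off. The three medians become 14.3–14.8, 15.5–16.0 and 16.9–17.4 months. Only the longest lead-in then exceeds 16.4. The gap between the axes stays at about 4.0 to 6.6 months.

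**4. Death wording.** Illustration: lead-in 5.5 months, time to progression exponential with mean 9 months from avelumab start. Suppose 2%, 5% or 9% of patients die off avelumab without recorded progression. Counting those deaths gives rwPFS-c medians of 11.5, 11.3 and 10.9 months; censoring them at death gives 11.7, 11.8 and 11.8. The differences are about 0.2, 0.5 and 0.9 month.

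**5. Censoring date.** Suppose 10% or 30% of event-free patients have a last visit before the last observation: 1 month before, 3 months before, or at a uniform 10–100% of their follow-up. Last-visit censoring then shortens the rwPFS median by 0.0 to 0.6 month and lowers the 12-month rate by about 0.2 to 4.2 percentage points. If the two dates coincide, the effect is nil.

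**The case against.** Protocol 9.8 allows the SAP to modify the protocol and requires an amendment only for major changes to primary endpoints. The SAP's rwPFS-c rule, which counts every death, is presumably the one that will be programmed, and it is the better one. This stands: the death conflict is a harmonisation fault, not evidence that deaths will be dropped. But the SAP does not say that it departs from the protocol here, so a reader cannot tell a decision from a slip.

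Last visit and last observation may be the same date for most patients. That also stands, and it limits the size of the point, not the need for one defined term.

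Stronger readings are tempting, but the documents do not support them:
- **The rwPFS-c observation period must exceed what is possible.** Step 3 shows that this depends on the lead-in and on censoring that the plan itself prescribes.
- **The protocol's death wording leaves some patients with no defined outcome.** Its censoring rule opens "If there were no clinical records of death or disease progression", and read literally an off-avelumab death is then neither an event nor censored. The natural reading is that no qualifying event was recorded. Aligning the death rule settles it either way.
- **The SAP reverted to superseded wording.** The protocol's amendment table shows visit replaced by observation in v4.1, but the SAP may have chosen its term. The mismatch rests on the current texts alone.
- **Progression before the first avelumab dose is mishandled.** No visible collection item dates such a progression, and a best response of PD is a category without a date. This is at most missing detail.
- **rwPFS-c is invalid because patients had to reach avelumab.** Protocol 8 and 9.3.1 and SAP 5.1 declare the cohort openly. rwPFS from avelumab start is a separate endpoint, and SAP 7.1 already tabulates chemotherapy duration and the treatment-free interval. No comparison with all chemotherapy starters is visible.

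**Conclusion.** The point holds in three parts, all from current text: the rwPFS-c death event differs between protocol and SAP; the censoring date differs for rwPFS and rwPFS-c when there is no later line; and SAP 8.1.4 measures the study's observation period on an axis that starts before that period does.

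The third part is wrong as written. It overstates follow-up by about the chemotherapy-to-avelumab lead-in: some 4.0 to 6.6 months for assumed median lead-ins of 4.0 to 6.5 months, against an index-date median of about 11.75 months under uniform entry. The 16.4-month ceiling follows from the documents' dates alone.

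For the first two parts the size cannot be fixed from the documents. Under the assumptions shown, the median moves by less than a month in either case, but other shares or handling would give other figures. All of this concerns secondary, descriptive endpoints. It should be corrected before the analysis is programmed; it does not touch the primary endpoint.

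**What to change.** 1. **Death rule.** Use death from any cause for rwPFS-c in both documents, by aligning Protocol 9.2.2 and 9.2.3.4 with SAP 5.5.
2. **Censoring date.** Use one defined date for rwPFS and rwPFS-c in both documents, and say which collected date supplies it. If it is the protocol's last observation date, state that a contact confirming survival only is not a progression assessment, since such a patient would be credited with progression-free time that nobody assessed. If it is the last visit, amend the protocol to match.
3. **Observation period.** Report it from the index date only. In SAP 8.1.4, delete the reverse Kaplan-Meier sentence or label its result as time since chemotherapy start.
4. **Optional.** Note beside the rwPFS-c curve that it is conditional on having started avelumab.

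The cost is wording in Protocol 9.2.2 and 9.2.3.4 (and 9.2.3.2 if the last visit is chosen) and in SAP 5.5 and 8.1.4, plus minor programming. The death rule and the observation period need no visible new data item. For the censoring date, the team should confirm that the chosen date is captured; Protocol 9.2.2 lists the date of last survival confirmation but, in its visible text, no separate last-visit date.

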Clinical stage classification: Bladder	Clinical stage is categorized using primary tumor (T factor), regional lymph nodes (N factor), distant metastasis (M factor) as follows. 
  
 Primary tumor (T factor)	Regional lymph nodes (N factor)	Distant metastasis (M factor)	Clinical stage	
   
 Ta	N0	M0	0a	
 
 Tis	N0	M0	0is	
 
 T1	N0	M0	I	
 
 T2a, T2b	N0	M0	II	
 
 T3a, T3b, T4a	N0	M0	IIIA	
 
 T1, T2a, T2b, T3a, T3b, T4a	N1	M0	IIIA	
 
 T1, T2a, T2b, T3a, T3b, T4a	N2, N3	M0	IIIB	
 
 T4b	Any N	M0	IVA	
 
 Any T	Any N	M1a	IVA	
 
 Any T	Any N	M1b	IVB	
  
	Primary tumor (T factor)	Regional lymph nodes (N factor)	Distant metastasis (M factor)	Clinical stage	Ta	N0	M0	0a	Tis	N0	M0	0is	T1	N0	M0	I	T2a, T2b	N0	M0	II	T3a, T3b, T4a	N0	M0	IIIA	T1, T2a, T2b, T3a, T3b, T4a	N1	M0	IIIA	T1, T2a, T2b, T3a, T3b, T4a	N2, N3	M0	IIIB	T4b	Any N	M0	IVA	Any T	Any N	M1a	IVA	Any T	Any N	M1b	IVB
Primary tumor (T factor)	Regional lymph nodes (N factor)	Distant metastasis (M factor)	Clinical stage																																										
Ta	N0	M0	0a																																										
Tis	N0	M0	0is																																										
T1	N0	M0	I																																										
T2a, T2b	N0	M0	II																																										
T3a, T3b, T4a	N0	M0	IIIA																																										
T1, T2a, T2b, T3a, T3b, T4a	N1	M0	IIIA																																										
T1, T2a, T2b, T3a, T3b, T4a	N2, N3	M0	IIIB																																										
T4b	Any N	M0	IVA																																										
Any T	Any N	M1a	IVA																																										
Any T	Any N	M1b	IVB																																										
Clinical stage classification:	Clinical stage is categorized using primary tumor (T																																												

Urethra	factor), reginal lymph nodes (N factor), distant metastasis (M factor) as follows.			

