6.3.2 Number of digits

Percentages will be rounded to 1 decimal place for the fraction distribution, unless the details of the individual items are specified. Among the summary statistics (number of subjects, mean standard deviation, minimum value, quartiles (25% point, 50% point [median], 75% point), and maximum value), the mean, standard deviation, and quartiles (25% point, 50% point [median], 75% point) are rounded up to where a decimal place is one digit below the original data.

7 Analysis of primary endpoints

7.1 Patient characteristics at baseline (at the start of the first-line chemotherapy and at the start of the avelumab administration)

Target : Analysis set

populatio

n

Endpoints : 1) Primary lesion at initial diagnosis

Categorical Variable

Site of the primary tumor
Histology of primary lesion¹⁾
Presence or absence of variant histology
 Subtype
Histologic dysplasia
 Two-step grade
 Three-step grade
Histological depth
Presence/absence of definitive treatment of primary lesion
 Treatment
 Surgery

2) At the start of the first-line chemotherapy

Continuous variable

Number of cycles of first-line chemotherapy
Number of cycles at the evaluation of best overall response to first-line chemotherapies
Treatment-free interval: Time from the end of first-line chemotherapy to the start date of avelumab administration (days)
Duration of first-line chemotherapy (days)

Categorical Variable

ECOG Performance Status
Karnofsky performance status (%)
Karnofsky performance status (2 divisions)
Bajorin risk classification
Staging (TNM classification)
 Primary tumor (T factor)
 Metastases to regional lymph nodes (N factor)
 Distant metastasis (M factor)
Clinical Stage
 Bladder
 Urethra
 Renal pelvis and ureter
Presence/absence of distant metastasis

distant metastasis site
Presence or absence of visceral metastasis
Presence or absence of non-visceral metastasis
Number of metastatic organs
Number of metastases in one organ
Number of distant metastases
Presence/absence of local recurrence
Regimen for first-line chemotherapy
Best overall response to first-line chemotherapies

3) At the start of avelumab administration

Continuous variable

Age

Categorical Variable

Gender
ECOG Performance Status
Karnofsky performance status (%)
Karnofsky performance status (2 divisions)
Bajorin risk classification
Staging (TNM classification)
 Primary tumor (T factor)
 Metastases to regional lymph nodes (N factor)
 Distant metastasis (M factor)
Clinical Stage
 Bladder

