Subtype	nested, including large nested/microcystic/micropapillary/lymphoepithelioma-like/plasmacytoid/signet ring cell/diffuse/sarcomatoid/giant cell/poorly differentiated/lipid-rich/clear cell/other
Histologic dysplasia	two step grades (low grade, high grade)/three step grades (G1, G2, G3)/unknown
Histologic dysplasia: two-step grade	low grade/high grade
Histologic dysplasia: three-step grade	G1/G2/G3
Histological depth	Bladder: pTX/pT0/pTa/pTis/pT1/pT2a/pT2b/pT3a/pT3bpT4a/pT4b Urethra: pTX/pT0/pTa/pTis/pT1/pT2/pT3/pT4 Renal pelvis: pTX/pT0/pTa/pTis/pT1/pT2/pT3/pT4 Ureter: pTX/pT0/pTa/pTis/pT1/pT2/pT3/pT4
Presence/absence of definitive treatment of primary lesion	absence/presence/unknown
Treatment	surgery/others
Surgery	Data will be aggregated based on the combination of the data obtained.
Gender	male/female
ECOG Performance Status	0/1/2/3/4
Karnofsky performance status (%)	100/90/80/70/60/50/40/30/20/10/0
Karnofsky performance status (2 divisions)	<80%/>=80%
Bajorin risk classification	0 (no risk factor)/1 (single risk factor)/2 (two risk factors)
Staging (TNM classification): Primary tumor (T factor)	Bladder: T0/Ta/Tis/T1/T2a/T2b/T3a/T3b/T4a/T4b/unknown

	n/other Urethra: T0/Ta/Tis/T1/T2/T3/T4/ unknown/other Renal pelvis: T0/Ta/Tis/T1/T2/T3/T4/ unknown/other Ureter: T0/Ta/Tis/T1/T2/T3/T4/unknown/other
Staging (TNM classification): Metastases to regional lymph nodes (N factor)	Bladder: N0/N1/N2/N3/unknown Urethra: N0/N1/N2/unknown Renal pelvis: N0/N1/N2/unknown Ureter: N0/N1/N2/unknown
Staging (TNM classification): Distant metastasis (M factor)	Bladder: M0/M1a/M1b/unknown/other Urethra: M0/M1/unknown/other Renal pelvis: M0/M1/unknown/other Ureter: M0/M1/unknown/other
Clinical Stage: Bladder	0a/0is/I/II/IIIA/IIIB/IVA/IVB
Clinical Stage: Urethra	0a/0is/I/II/III/IV
Clinical Stage: Renal pelvis	0a/0is/I/II/III/IV
Clinical Stage: Ureter	0a/0is/I/II/III/IV
Presence/absence of distant metastasis	presence/absence/unknown
Site of distant metastasis	lung/liver/adrenal/pancreas/kidney/spleen/bone/ distant lymph nodes/other
Presence or absence of visceral metastasis	presence/absence
Presence or absence of non-visceral metastasis	presence/absence
Number of metastatic organs	Single organ metastasis/multiple organ metastasis
Number of metastases in one organ	single/multiple
Number of distant metastases	single ("single organ metastasis" and "single")/multiple ("multiple organ metastasis" + "single organ metastasis" and "multiple")

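### The SAP's clinical-stage tables give no stage to T0 N0 M0 at any primary site, and the stage variable has no level in which to count such patients

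*SAP*

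**What the plan says.** SAP 5.5 introduces the bladder stage table with the rule "Clinical stage is categorized using primary tumor (T factor), regional lymph nodes (N factor), distant metastasis (M factor) as follows". The urethra table and the shared renal pelvis/ureter table open in the same way. Each starts at Ta and lists the T, N, M combinations that lead to each stage. T0 can enter only through rows open to any T, such as "Any T Any N M1a IVA" for bladder.

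SAP 7.1 sets the permitted values. Besides unknown and other, the bladder T factor takes "T0/Ta/Tis/T1/T2a/T2b/T3a/T3b/T4a/T4b". The other sites are "Urethra: T0/Ta/Tis/T1/T2/T3/T4/ unknown/other", "Renal pelvis: T0/Ta/Tis/T1/T2/T3/T4/ unknown/other" and "Ureter: T0/Ta/Tis/T1/T2/T3/T4/unknown/other". The bladder stage divisions are "0a/0is/I/II/IIIA/IIIB/IVA/IVB"; the other sites use 0a, 0is, I, II, III and IV. T, N and M each have an unknown level. Clinical stage has none.

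Stage is listed among the items at chemotherapy start and again under "3) At the start of avelumab administration". Protocol 9.2.1 asks for the latest data before each of those starts, so the second staging describes patients after chemotherapy. SAP 5.2 treats absent data as missing, without imputation.

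**The concern.** A lookup rule should return a result for every input that the plan permits. This one fails on inputs with nothing missing: T, N and M are all recorded, yet the derived stage is empty. The stage table then cannot separate a patient known to have no residual disease from one whose TNM was never charted.

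T0 N0 M0 is a foreseeable value at avelumab start. Complete response is a permitted best response to chemotherapy in SAP 7.1, and definitive treatment of the primary lesion is collected. Describing baseline disease characteristics is the primary objective, so this table is core output. The set of staged patients may also differ between the two time points, which would weaken any comparison of the two stage distributions.

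**Working it through.** The plan states no figure to reproduce. The check runs every T x N x M combination permitted by SAP 7.1 (leaving aside unknown and other) through the SAP 5.5 rows.

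**Inputs (SAP 7.1)**
- Bladder: 10 T values, 4 N values (N0 to N3), 3 M values (M0, M1a, M1b).
- Urethra, renal pelvis and ureter: 7 T values, 3 N values (N0 to N2), 2 M values (M0, M1).

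**Distant metastasis present.** Every table has a row for any T and any N with M1 (M1a and M1b for bladder), so no M1 combination is unstaged. All gaps lie at M0.

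**Cells at M0**

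| Table | T x N cells | Staged | Unstaged | Unstaged combinations |
|---|---|---|---|---|
| Bladder | 10 x 4 = 40 | 30 | 10 | T0 with N0-N3 (4), Ta with N1-N3 (3), Tis with N1-N3 (3) |
| Urethra | 7 x 3 = 21 | 16 | 5 | T0 N0, T0 N1, Ta N1, Tis N1, T2 N0 |
| Renal pelvis/ureter | 7 x 3 = 21 | 20 | 1 | T0 N0 |

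Over all M values the counts are 10 of 120 (10 x 4 x 3), 5 of 42 (7 x 3 x 2) and 1 of 42.

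**T0 alone, over all M values.** Unstaged: bladder 4 of 12, urethra 2 of 6, renal pelvis/ureter 1 of 6. The remaining T0 combinations are staged through the any-T rows: M1 at every site, and at M0 also N2 for urethra and N1 or N2 for renal pelvis/ureter. T0 N0 M0 is the one combination unstaged in all three tables.

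**Conflicting rows.** In the urethra table T2 N1 M0 matches both stage II and stage III, while T2 N0 M0 matches nothing. No other combination in any table matches two stages.

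**Effect on the percentages.** Take one primary site at avelumab start. Let p be the share of all its patients in a given stage and f the share that is T0 N0 M0 (ignoring other unstaged cells).
- Missing values left out: the reported share is p / (1 - f), which exceeds p for any f above 0. Every listed stage is inflated by the same factor, and the patients removed are those with no recorded disease.
- All patients with that site kept: the reported share stays p, and the rows add up to 1 - f with no line to explain the shortfall.

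SAP 7.1 does not choose between these. It promises numbers and proportions for categorical variables, and names neither a denominator nor a missing row. The count of missing subjects in SAP 6.3.1 belongs to the summary statistics, which SAP 7.1 applies to continuous variables. The documents give neither f nor p.

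**The case against.** The strongest reply is that this is an incomplete lookup table with no demonstrated bias. Much of that stands.

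- **Denominator.** Removing missing values from the denominator is written only for ORR (SAP 8.1.3). The target population in SAP 7.1 is the analysis set; with a full denominator no stage percentage moves.
- **Information retained.** Affected patients stay in the analysis set. T (with T0 as its own level), N, M, distant metastasis and best response to chemotherapy are tabulated separately. The study is descriptive, and no visible analysis takes clinical stage as an input.
- **Frequency.** The counts above are table cells, which say nothing about how many patients fall in them. Entry requires locally advanced or metastatic disease (Protocol 9.3.1), and T0 with M1 is staged. SAP 7.1 lists definitive treatment under the primary lesion at initial diagnosis, so the documents do not show how often surgery precedes avelumab. Nor do they say that charts re-record T as T0 after response or resection.

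A reader might infer that the patients who did best are systematically removed and that the published stage IV share will be too high. The documents do not support that. It needs a denominator rule that SAP 7.1 does not contain and frequencies that appear nowhere. It also fits T0 N0 M0 only: the unstaged bladder cells with N1 to N3 are node-positive disease, and losing them need not shift the picture in the same direction.

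The reply does not rescue the derivation itself. The SAP permits T0, tabulates stage at a post-chemotherapy time point, and provides neither a row nor a level for the result. A staging system may well have no group for T0 N0 M0; the table still has to count the patient somewhere.

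**Conclusion.** The point holds as a defect in the specification of a primary-endpoint item. T0 N0 M0 has no stage at any site, and further M0 combinations are unstaged for bladder and urethra. Patients with complete TNM become missing in the clinical-stage rows, and in those rows only.

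The cell counts follow from the SAP's own value lists and rows, and need no outside assumption. The distortion at avelumab start is conditional: it requires that missing values be excluded from the percentages and that some patients be recorded as T0 N0 M0. Its size cannot be computed from the documents. The contradiction between the urethra T2 rows stands on the text alone.

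**What to change.** In SAP 5.5 and in the SAP 7.1 divisions, add two levels to each clinical-stage variable: no evidence of disease (T0 N0 M0), and not classifiable from recorded TNM. Assign every permitted combination without a listed stage to one of them. Of the unstaged cells, the first level takes one in each table. The second takes the other 9 for bladder and up to 4 for urethra, depending on how T2 N0 is resolved. It should also take combinations with an unknown or other value that match no row.

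State in SAP 7.1 that the denominator is all patients with that primary site, at both time points.

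In the same edit, reconcile the two urethra rows so that T2 N1 M0 leads to a single stage and T2 N0 M0 is assigned.

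The cost is a few rows in the derivation tables and the table shell. No new data are needed, and no stage has to be invented for T0 N0 M0.
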